### 9.1.3. Double-blind Treatment Phase

After the baseline visit, subjects will return for study visits at the end of Weeks 2, 4, 8, 12, 24, 36, and 48 (scheduled relative to the baseline visit date). After Week 48, subjects will continue to take their blinded study drug and attend visits every 12 weeks until all subjects have reached Week 48 and treatment assignments have been unblinded. Provided the results from the primary analysis do not preclude (further) exposure of subjects to D/C/F/TAF, all subjects will return to the clinic for an unblinding visit, preferably at the next planned visit.

The time window for the Week 2 visit is  $\pm 2$  days, and for the visits through the unblinding visit is  $\pm 7$  days of the protocol-specified visit date. The following procedures are to be completed and documented at each visit.

- Review of AEs and changes in concomitant medications.
- Complete physical examination at Weeks 24, 48, and at the unblinding visit (urogenital/anorectal examinations will be performed at the discretion of the investigator).
- Symptom-directed physical examination (physical examination of body parts for which symptoms have been reported by the subject) as needed at Weeks 2, 4, 8, 12, 36, and every 12 weeks following Week 48 until unblinding.
- Vital signs measurement (blood pressure and pulse) and weight.
- Midstream urine sample collection for the following laboratory procedures:
  - Urinalysis and urine chemistry (see also Section 9.1.2.1).
  - Urine renal biomarkers (fasted, ie, no food or drinks, except water, at least 8 hours prior to urine collection; if the subject has not fasted prior to the visit, the visit may proceed, but the subject must return within 72 hours in a fasted state to provide a urine sample for renal biomarkers) at Weeks 2, 4, 12, 24, 48, every 12 weeks following Week 48 until and including the unblinding visit (see also Section 9.1.2.2).
  - Urine pregnancy test (females of childbearing potential only); positive urine pregnancy tests will be confirmed with a serum test; if this test is positive, the subject will be withdrawn (see also Section 12.4.3).

- Blood sample collection for the following laboratory analyses:
  - Chemistry profile (see also Section 9.1.2.1). At Weeks 24 and 48, analysis of glucose will be done as part of the fasting metabolic profile and not as part of the chemistry profile.
  - Metabolic profile (including glucose; collected fasted; if the subject has not fasted prior to the visit, the visit may proceed, but the subject must return within 72 hours in a fasted state to have a blood draw for the metabolic assessments) at Weeks 24, 48, every 12 weeks following Week 48 until and including the unblinding visit (see also Section 9.1.2.1).
  - Hematology profile (see also Section 9.1.2.1).
  - Cystatin C and eGFRcystatin according to the CKD-EPI formula.
  - eGFRcreatinine according to the Cockcroft-Gault formula, and the CKD-EPI formula (for details, see Section 9.5.4).
  - Plasma HIV-1 RNA.
  - CD4+ cell count.
  - HIV-1 resistance testing. HIV-1 PR/RT genotype/phenotype testing will be requested by the study virologist on samples from subjects eligible for resistance testing.
  - Plasma storage sample for possible additional clinical testing at Weeks 2, 4, 12, 24, 36, 48, and the unblinding visit.
  - PBMC storage sample at Weeks 24 and 48, for exploratory analysis (eg to characterize archived viral resistance) if deemed necessary by the study virologist.
- Pharmacokinetic sample collection:
  - Blood samples will be collected at least 30 minutes to maximum 4 hours postdose at Weeks 2, 4, 12, 24, and 48.
  - Blood samples will be collected at 2 time points with at least 2.5 hours in between sampling at Weeks 8 and 36. The first pharmacokinetic sample at these visits should be taken between 1 and 4 hours postdose (dosing may occur prior to the study site visit).
- Document study drug dispensation and accountability (except at Week 2) for all study drugs dispensed.
- Checking of the study medication log booklet for review of treatment adherence.

In subjects participating in the bone investigation substudy:

• Bone biomarkers at Weeks 2, 4, 12, 24, 48, and Week 72 (if applicable) (collected fasted, ie, no food or drinks, except water, at least 8 hours prior to sample collection): CTX, P1NP, PTH and 25-hydroxy vitamin D. Biomarkers PTH and 25-hydroxy vitamin D should be assessed at Weeks 24 and 48 only. If the subject has not fasted prior to the

visit, the visit may proceed but the subject must return within 72 hours in a fasted state to provide a blood sample for bone biomarker assessment.

• DXA scan of spine and hip at Weeks 24 and 48. A time window of  $\pm 2$  weeks and a rescan for technical reasons within 4 weeks are allowed.

## 9.1.4. Open-label Single-arm Phase

After the unblinding visit, provided the results from the primary analysis do not preclude (further) exposure of subjects to D/C/F/TAF, subjects will receive the D/C/F/TAF FDC tablet in an open-label single-arm treatment phase of the study and will be required to attend visits every 12 weeks. Subjects from the control arm who switch to the D/C/F/TAF treatment after the 48-week double-blind treatment will be required to return to the clinic for an additional visit 3 to 7 weeks after the unblinding visit. If the additional visit would take place within a  $\pm 4$  week window of a normal planned schedule visit, the additional visit can take place during a planned visit.

The time window for the visits during the open-label single-arm treatment phase is ±7 days of the protocol-specified visit date, except for the additional visit where no extra time window is applicable. The following evaluations are to be completed and documented at each visit.

- Review of AEs and changes in concomitant medications.
- Symptom-directed physical examination (physical examination for which symptoms have been reported by the subject) as needed at **3 to 7 weeks following the unblinding visit** (only for those subjects who switched to D/C/F/TAF), every **12 weeks following the unblinding visit until and including Week 96.**
- Vital signs measurement (blood pressure and pulse) and weight.
- Midstream urine sample collection for the following laboratory procedures:
  - Urinalysis and urine chemistry (see also Section 9.1.2.1).
  - Urine renal biomarkers (fasted, ie, no food or drinks, except water, at least 8 hours prior to urine collection; if the subject has not fasted prior to the visit, the visit may proceed, but the subject must return within 72 hours in a fasted state to provide a urine sample for renal biomarkers) at 3 to 7 weeks following the unblinding visit (only for those subjects who switched to D/C/F/TAF), every 12 weeks following the unblinding visit until and including Week 96 (see also Section 9.1.2.2).
  - Urine pregnancy test (females of childbearing potential only); positive urine pregnancy tests will be confirmed with a serum test. If the test is positive, the subject will be withdrawn (see also Section 12.4.3).
- Blood sample collection for the following laboratory analyses:
  - Chemistry profile (see also Section 9.1.2.1).

- Metabolic profile (including glucose; collected fasted; if the subject has not fasted prior to the visit, the visit may proceed, but the subject must return within 72 hours in a fasted state to have a blood draw for the metabolic assessments) at Week 96 (see also Section 9.1.2.1).
- Hematology profile (see also Section 9.1.2.1).
- Cystatin C and eGFRcystatin according to the CKD-EPI formula at 3 to 7 weeks following the unblinding visit (only for those subjects who switched to D/C/F/TAF) (for details, see Section 9.5.4).
- eGFRcreatinine according to the Cockcroft-Gault formula and the CKD-EPI formula (for details, see Section 9.5.4).
- Plasma HIV-1 RNA.
- CD4+ cell count.
- HIV-1 resistance testing. HIV-1 PR/RT genotype/phenotype testing will be requested by the study virologist on samples from subjects eligible for resistance testing.
- Plasma storage sample for possible additional clinical testing at 3 to 7 weeks following the unblinding visit (only for those subjects who switched to D/C/F/TAF) and at Week 96.
- PBMC storage sample at Week 96 for exploratory analysis (eg to characterize archived viral resistance) if deemed necessary by the study virologist.
- Document study drug dispensation and accountability for all study drugs dispensed.
- Checking of the study medication log booklet for review of treatment adherence.

In subjects participating in the bone investigation substudy:

- Bone biomarkers at **3 to 7 weeks following the unblinding visit** (only for those subjects who switched to D/C/F/TAF) and **every 24 weeks until and including Week 96** (collected fasted, ie, no food or drinks, except water, at least 8 hours prior to sample collection): CTX, and P1NP. Biomarkers PTH and 25-hydroxy vitamin D should be assessed at **Week 96** only. If the subject has not fasted prior to the visit, the visit may proceed but the subject must return within 72 hours in a fasted state to provide a blood sample for bone biomarker assessment.
- DXA scan of spine and hip at **Week 96**. A time window of ±2 weeks and a rescan for technical reasons within 4 weeks is allowed.

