## **Secondary Endpoints**

The secondary endpoints of this study are:

- The proportion of subjects with HIV-1 RNA <50 copies/mL at Week 96 as defined by the FDA snapshot analysis;
- The proportion of subjects with HIV-1 RNA <20 and <200 copies/mL at Weeks 48 and 96 as defined by the FDA snapshot analysis;
- The proportion of subjects with HIV-1 RNA <20, <50, and <200 copies/mL at Weeks 48 and 96 as defined by the time to loss of virologic response (TLOVR) algorithm;
- The change from baseline in log10 HIV-1 RNA at Weeks 48 and 96;
- The change from baseline in CD4+ cell count at Weeks 48 and 96;
- The change from baseline in serum creatinine, eGFRcreatinine (by Cockcroft-Gault and by CKD-EPI) and eGFRcvstatin C (by CKPD-EPI) at Weeks 48 and 96;
- The proportion of subjects experiencing grade 3 and 4 AEs, SAEs, and premature discontinuations due to AEs through Weeks 48 and 96.
- The change from baseline in renal biomarkers at Week 48 and 96;
- The development of viral resistance through Weeks 48 and 96;
- Pharmacokinetic parameters (by population pharmacokinetic analysis) for DRV and TAF.

The endpoints of the bone investigation substudy are:

- The percentage change from baseline in hip and spine BMD and change from baseline in T-score at Weeks 24, 48, and 96;
- The change from baseline in bone biomarkers at Weeks 24, 48, and 96.

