## **Safety Analyses**

The original terms used by investigators to identify AEs will be coded using the Medical Dictionary for Regulatory Activities (MedDRA). All reported AEs with onset during the study will be included in the analysis. For each AE, the percentage of subjects who experience ≥1 occurrence of the given event will be summarized.

Summaries (number and percentage of subjects) of treatment-emergent AEs (by system organ class [SOC] and preferred term [PT]) will be provided by treatment arm. Additional summaries will include summaries for AEs by severity grade (with special attention to grade 3 or 4 AEs), investigator's assessment of relationship to treatment, SAEs, and AEs leading to discontinuation of study treatment.

Laboratory data will be summarized by treatment arm and type of test. Descriptive statistics will be calculated for each laboratory analyte for observed values and changes from baseline at each scheduled time point. Graphical presentation of changes in laboratory parameters can be made as applicable. Abnormalities will be determined according to the Division of AIDS (DAIDS) grading table and in accordance with the normal ranges of the clinical laboratory. Maximum toxicity grade after baseline will be tabulated and special attention will be given to the subjects who developed grade 3 or 4 toxicities.

The changes from baseline in serum creatinine, eGFRcreatinine (by Cockcroft-Gault and by CKD-EPI) and eGFRcystatin C (by CKPD-EPI) at Weeks 48 and 96 will be summarized by treatment arm and using descriptive statistics. The difference in changes from baseline at Week 48 in serum creatinine between the 2 treatment arms will be tested using ANCOVA, including baseline serum creatinine in the model.

16

17

Selected renal biomarkers, including retinol binding protein and beta-2-microglobulin, will be summarized by treatment arm and visit using descriptive statistics. The difference in change from baseline in these biomarkers at Week 48 between 2 treatment arms will be tested using the Wilcoxon rank-sum test.

Descriptive statistics of vital signs (pulse rate, systolic and diastolic blood pressure) values and changes from baseline will be summarized at each scheduled time point. The percentage of subjects with values beyond clinically important limits will be tabulated.

Physical examination findings and changes from baseline at each scheduled time point will be listed.

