# TIME AND EVENT SCHEDULE

PERIOD				7	Active	ble-bli -contro ent Pe	olled		Open-label Single-arm D/C/F/TAF Treatment Period f			Extension Period h		30- Day FU j	
Visit	Screening		Week 2	Week 4	Week 8	Week 12	Week 24	Week 36	Week 48 d and Unblinding Visit e	3-7 weeks after Unblinding Visit g	Every 12 weeks	Week 96	Every 6 months		
Study Procedures															
Screening/Administrat	ive														
Informed consent k	X														
Medical history	X														
12-Lead ECG (local)	X														
Height	X														
HBV and HCV testing															
Serum pregnancy test 	X														
FSH test m	X														
Inclusion/exclusion	X														
criteria															<del>  </del>
Check clinical status n	 	X													
Study Drug Administra	ation		1	ı	1	1	ı		T	T		T	1	I	
Randomization o		X													<del></del>
Adherence (log booklet) p		X	X	X	X	X	X	X	$X^q$	X	X	X		X	
Drug dispensation & accountability		X		X	X	X	X	X	$X^{q,r}$	X s	X	X	X t	Xs	
Safety Evaluations															
Adverse events	X	X	X	X	X	X	X	X	X q	X	X	X	X	X	X
Vital signs and weight		X	X	X	X	X	X	X	$X^{q}$	X	X	X	X	X	Xu
Complete physical examination	X	X	71	71	21	21	X	21	X	71	71	21	71	X	71
Symptom-directed									X/						
physical examination			X	X	X	X		X	X v	X	X	X	X		X
Concomitant medications	X	X	X	X	X	X	X	X	$X^q$	X	X	X	X	X	X

PERIOD			Ι		Dou Active Treatm		olled	T	Open-label Single-arm D/C/F/TAF Treatment Period f			Extension Period h	ESTD i	30- Day FU j	
	Screeninga	Baseline Day 1 b	Week 2	Week 4	Week 8	Week 12	Week 24	Week 36	Week 48 d and Unblinding Visit e	3-7 weeks after Unblinding Visit g	Every 12 weeks	Week 96	Every 6 months		
Clinical Laboratory Ev	aluations w														
Chemistry profile x	X	X	X	X	X	X	X	X	$X^q$	X	X	X	X	X	X
Metabolic profile y		X					X		$X^{q}$			X			1
Hematology profile z	X	X	X	X	X	X	X	X	$X^{q}$	X	X	X	X	X	X
Cystatin C and eGFR cystatin C	X	X	X	X	X	X	X	X	$X^q$	X					
eGFR creatinine aa	X	X	X	X	X	X	X	X	$X^q$	X	X	X	X	X	X
Urinalysis and urine chemistry bb	X	X	X	X	X	X	X	X	$X^q$	X	X	X	X	X	X
Urine pregnancy test k		X	X	X	X	X	X	X	$X^q$	X	X	X	X	X	X

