- Once all subjects have reached Week 48 and unblinded treatment assignments have been provided to the investigators, all subjects will return to the clinic for an unblinding visit, preferably at the next planned visit. At the unblinding visit, provided the results from the primary analysis do not preclude (further) exposure of subjects to D/C/F/TAF, all subjects will discontinue their blinded study drugs and will receive the D/C/F/TAF FDC tablet in a single-arm treatment period up to Week 96.
- Study visits during the open-label single-arm D/C/F/TAF treatment period are to be completed within  $\pm 7$  days of the protocol-specified visit date.
- Subjects from the control arm who switch to the D/C/F/TAF treatment after the 48-week double-blind treatment will be required to return to the clinic for an additional visit 3 to 7 weeks after the unblinding visit. If this additional visit would take place within a ±4 week window of a normal planned schedule visit, the additional visit can take place during this planned visit.
- Visits in the extension period will occur every 6 months, until the D/C/F/TAF treatment becomes commercially available and is reimbursed, or can be accessed through another source in the country where he/she is living, or until the sponsor terminates clinical development. Study visits during the extension period are to be completed within ±14 days of the protocol-specified visit date.
- ESTD visit to occur within 72 hours of last dose of study treatment for subjects who prematurely discontinue, either during the double-blind treatment period (from Day 1 to Week 48), or during the open-label single-arm D/C/F/TAF treatment period (between Week 48 and Week 96).
- Required for any subject who has an ongoing AE or SAE at the time of his/her study visit (unless consent is withdrawn); ±7 days window may be used.
- k Signing of the ICF needs to be done before the first study-related activity.
- Females of childbearing potential only. Additional serum or urine pregnancy tests may be performed, as determined necessary by the investigator or required by local regulation, to establish the absence of pregnancy throughout the study. Findings during these unscheduled visits or assessments need to be reported in the eCRF.
- m FSH test for female subjects who have stopped menstruating for at least 2 years but do not have documentation of ovarian failure.

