- n If a subject's clinical status changes (including available laboratory results or receipt of additional medical records) after screening but before the first dose of study drug is given such that he or she no longer meets all eligibility criteria, then the subject should be excluded from participation in the study.
- Randomization should be performed during the baseline visit, provided that all screening procedures have been completed and subject eligibility has been confirmed
- Dispensation of the study medication log booklet at the baseline visit, in which study medication intakes need to be recorded; checking of the log booklet and discussion with the subject by the investigator or designated study personnel at all subsequent visits.
- q At Week 48, every 12 weeks following Week 48 until unblinding, and the unblinding visit.
- The first open-label study drug dispensation will occur at the unblinding visit.
- brug accountability only; study drug will not be dispensed at this visit.
- t Subjects might return to the clinic more frequently during the extension period for drug dispensation only.
- u Weight only.

- A symptom-directed physical examination (physical examination of body parts for which symptoms have been reported by the subject) will be performed as needed at the every 12 weeks visits between Week 48 and the unblinding visit.
- Week 8 and 36 visits, where fasting is not required).
- Chemistry profile: alpha1-acid glycoprotein (AAG), alkaline phosphatase (ALP), aspartate aminotransferase (AST), alanine aminotransferase (ALT), gamma-glutamyl transferase (GGT), total bilirubin, direct and indirect bilirubin, total protein, albumin, creatine phosphokinase (CPK), bicarbonate, blood urea nitrogen (BUN), chloride, creatinine, glucose, phosphorus, potassium, sodium, uric acid, amylase (reflex lipase testing is performed in subjects with total amylase >1.5xULN). At baseline, Weeks 24, 48, and 96, analyses of glucose will be done as part of the fasting metabolic assessments and not as part of the chemistry profile.
- Fasting metabolic profile (total, high-and low-density lipoprotein [HDL and LDL] cholesterol, triglycerides, glucose). If a subject has not fasted prior to the visit, the visit may proceed, but subject must return within 72 hours in a fasted state to have a blood draw for the metabolic assessments.

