## **Serum Creatinine and Cystatin C**

The changes from baseline in serum creatinine, eGFRcreatinine (by Cockcroft-Gault and by CKD-EPI) and eGFRcystatin (by CKPD-EPI) at Weeks 48 and 96 will be summarized by treatment arm and using descriptive statistics. The difference in changes from baseline at Week 48 in serum creatinine between the 2 treatment arms will be tested using ANCOVA, including baseline serum creatinine in the model.

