5.2.3. Creatinine and Glomerular Filtration

5.2.3.1. Serum Creatinine and Cystatin C

Estimated glomerular filtration rate based on the creatinine clearance will be calculated according to the Cockcroft-Gault formula (eGFRcr_{CKD-EPI}) and the CKD-EPI formula (eGFRcr_{CKD-EPI}) and eGFR based on cystatin C clearance will be calculated according to the CKD-EPI formula (eGFRcyst_{CKD-EPI}).

- eGFRcr according to the Cockcroft-Gault formula (unit: mL/min):

Male: $(140 - age in years) \times (weight in kg) = eGFRcr_{CG}(mL/min)$

 $72 \times (\text{serum creatinine in mg/dL})$

Female: $(140 - \text{age in years}) \times (\text{weight in kg}) \times 0.85 = \text{eGFRcr}_{CG} \text{ (mL/min)}$

 $72 \times (\text{serum creatinine in mg/dL})$

- eGFRcr and eGFRcyst according to the CKD-EPI formula (unit: mL/min/1.73m²):

eGFRcr_{CKD-EPI}

Female: $Scr \le 0.7 \text{ mg/dL}$ 144 x $(Scr/0.7)^{-0.329}$ x 0.993^{age}

Scr > 0.7 mg/dL 144 x $(Scr/0.7)^{-1.209}$ x 0.993^{age}

Male: $Scr \le 0.9 \text{ mg/dL}$ 141 x $(Scr/0.9)^{-0.411}$ x 0.993^{age}

Scr >0.9 m	ng/dL 14	1 x (Scr/0.9) ^{-1.209} x 0.993 ^{age}
eGFRcyst _{CKD-EPI}		
Scyst ≤0.8	mg/L 13	3 x (Scyst/0,8) ^{-0.499} x 0.996 ^{age} [x 0.932 if female]
Scyst >0.8	mg/L 13	3 x (Scyst/0,8) ^{-1.328} x 0.996 ^{age} [x 0.932 if female]

Scr = serum creatinine (mg/dL), Scyst = serum cystatin C (mg/L)

The changes from reference in serum creatinine, eGFRcr_{CG} and eGFRcr_{CKD-EPI} and eGFRcyst_{CKD-EPI} at Week 96 will be summarized by treatment arm and using descriptive statistics.

Within-treatment arm comparison versus reference at Week 96 will be assessed using Wilcoxon signed-rank test.

Stages of GFR at reference versus the minimum post-reference GFR value and the last available value will be summarized by count and percent of subjects. Kidney disease stages are defined as follows: 1 (Normal): $GFR \ge 90$; 2 (Mild): GFR 60-89; 3 (Moderate): GFR 30-59; 4 (Severe): GFR 15-29; 5 (Renal Failure): GFR < 15 mL/min).

In addition to the above, the number and proportion of subjects with a >25%, >50% and >75% decrease from reference will be tabulated.

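### Week 96 change in eGFR-cystatin C is a secondary endpoint, but after unblinding the schedule plans no cystatin C in the Initial D/C/F/TAF arm and only one sample, at 3 to 7 weeks, in switchers

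*Protocol*

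**What the plan says.** **What is promised.** The secondary endpoints in the Protocol Synopsis and in Section 11.1 include change in eGFR-cystatin C "by CKPD-EPI) at Weeks 48 and 96". The Synopsis safety analyses and Section 11.6 carry this into the analysis: "by CKPD-EPI) at Weeks 48 and 96 will be summarized by treatment arm". SAP 5.2.3.1 repeats the Week 96 summary by arm for serum creatinine, both creatinine-based eGFRs and eGFR-cystatin C. It then adds: "Within-treatment arm comparison versus reference at Week 96 will be assessed using Wilcoxon signed-rank test". That sentence names no variable, but it follows directly on the list.

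**What is sampled.** Under blinded treatment cystatin C is drawn at every visit. Footnote q of the Time and Event Schedule continues this: "At Week 48, every 12 weeks following Week 48 until unblinding, and the unblinding visit". After that, Section 9.1.4 plans it "according to the CKD-EPI formula at 3 to 7 weeks following the unblinding visit (only for those subjects who switched to D/C/F/TAF"). The schedule row headed "Cystatin C and eGFR"-cystatin agrees: its last mark is under the 3-to-7-week visit, with nothing under the 12-weekly open-label visits, Week 96, the extension, early discontinuation or follow-up. The creatinine-based eGFR row directly below is marked in all of those columns.

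**Other relevant text.** Section 9.5.4 says that eGFR-cystatin C is followed over the treatment phase, without naming visits. It also has cystatin C measured at the repeat test after a creatinine-based eGFR below 50 mL/min.

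**The concern.** A secondary endpoint is defined, and its analysis written, at a visit where the measurement is not scheduled. Followed as written, the Week 96 table would carry arm labels. Its entries would come only from subjects whose enrolment was late enough for blinded sampling, or the post-switch visit, to run into the Week 96 window.

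The gap matters most in the Initial D/C/F/TAF arm, which has the longest exposure to the test product. SAP 2.6 sets its reference at the pre-treatment baseline. Protocol 1.3 explains that cobicistat raises serum creatinine by blocking its secretion, without changing true filtration. The Week 96 creatinine-based change in this arm therefore contains that effect. Cystatin C is the other eGFR measure the plan offers, and this arm has no scheduled sample of it after unblinding.

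**Working it through.** There is no stated figure to reproduce. The check is whether any scheduled cystatin C sample can land in the SAP's Week 96 window.

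**Inputs**
- Week 96 analysis window: Day 631 to 714 (SAP 2.2.2).
- Target day = 7 × week + 1, so Week 60 = 421, Week 72 = 505, Week 84 = 589 and Week 96 = 673 (SAP 2.2.2).
- Extra visit, control-arm switchers only: 3 to 7 weeks, that is 21 to 49 days, after unblinding (Protocol 9.1.4).
- Visit tolerance: ±7 days. The extra visit may be merged with a planned visit within ±4 weeks (Protocol 9.1.4).
- Timing of unblinding: "all subjects will return to the clinic for an unblinding visit, preferably at the next planned visit" (Time and Event Schedule).
- Data scope: up to each subject's Week 96 visit, apart from DXA and confirmatory virology (SAP 2.2.1).

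**Scheduled cystatin C in the window, by unblinding visit**

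| Unblinding visit | Initial arm, last sample | Initial arm, in window | Switchers, extra-visit days | Switchers, in window |
|---|---|---|---|---|
| Week 60 | Day 421 | 0 | 421+21 to 421+49 = 442–470 | 0 |
| Week 72 | Day 505 | 0 | 505+21 to 505+49 = 526–554 | 0 |
| Week 84 | Day 589 | 0 | 589+21 to 589+49 = 610–638 | 0 or 1 |
| Week 96 | Day 673 | 1 | 694–722, after the Week 96 visit and out of scope | 1, from the unblinding visit, on control |
| Still blinded | Week 96 visit | 1 | none yet | 1, on control |

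**Sensitivity to visit windows**
- Latest Week 72 unblinding is 505 + 7 = Day 512. The extra visit is then Day 533–561, still before Day 631.
- Week 84 unblinding on target: the overlap is Day 631–638, which is 8 of the 29 permitted days. If unblinded on Day 582 it is 1 of 29; on Day 596, 15 of 29.
- Earliest unblinding at which a switcher's extra visit can reach the window: 631 − 49 = Day 582 (Week 83).
- Merging the extra visit with the earliest Week 96 visit (673 − 7 = Day 666) needs unblinding on or after 666 − 28 − 49 = Day 589, so it does not lower that bound.
- In the Initial arm, unblinding must itself fall on Day 631 or later.

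The Day 582 and Day 631 bounds hold whether or not unblinding takes place at a planned visit.

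**Which regimen the values describe.** Late Switch values taken while blinded, or at the unblinding visit, are on the control regimen. Only an extra-visit sample falling in the window gives a change after the switch.

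**The case against.** The strongest case is that the sampling was intended and the wording is loose. The table and Section 9.1.4 agree with each other: full cystatin C sampling during the blinded comparison, then one targeted sample after the change from TDF to TAF. The objective that names eGFR-cystatin C is set at Week 48. The Week 96 time point may simply have been attached to a list of three renal measures. That may well be so, but the endpoint, analysis and SAP text would then still need correcting.

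Second, little inference depends on it. SAP 1.3 tests no formal hypothesis at Week 96, and retinol binding protein, beta-2-microglobulin, the urine protein and albumin ratios and phosphate excretion all remain. This stands and limits the consequence.

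Third, the cobicistat effect appears within days, so blinded cystatin C data already separate it from true filtration in the Initial arm. This stands up to unblinding. It does not supply a Week 96 value.

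Fourth, other routes to a value exist. The test triggered below 50 mL/min yields a selected group. Leftover viral-load samples and stored plasma may be used for further safety testing, but no cystatin C assay is planned on them. The SAP's GFR-stage tables by minimum and last available value need no Week 96 draw, but they are a different summary.

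Fifth, adding a test may come too late. The SAP, dated April 2018, refers back to the Week 48 analysis, and the protocol's COVID-19 appendix deals only with the 6-monthly extension visits. This stands for subjects already past Week 96 and affects which fix is available, not whether the mismatch exists.

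**Conclusion.** The concern holds. After unblinding, scheduled cystatin C amounts to 0 samples per Initial-arm subject and 1 per switcher. Subjects unblinded at Week 60 or 72 have no scheduled value in the Week 96 window. Those unblinded at Week 84 have none in the Initial arm and at most one as switchers. A Week 96 eGFR-cystatin C result would therefore describe a subset determined by enrolment date, partly on the wrong regimen in the Late Switch arm.

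This assumes that the schedule is followed as written. The SAP provides for subjects who do not switch before Week 96, but neither document gives their number or any calendar of unblinding, so no percentage of subjects can be stated. The Week 48 eGFR-cystatin C objective, the other Week 96 renal measures and the primary conclusion are unaffected.

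**What to change.** Add cystatin C and eGFR-cystatin C to the Week 96 column of the Time and Event Schedule and to the Week 96 assessments in Section 9.1.4. The cost is one analyte on an existing blood draw and a short amendment, with no extra visit or procedure.

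For subjects already past Week 96, the plasma stored at that visit could be assayed. Section 9.1.1 already allows additional safety testing on it. This is sound only if the assay is shown to be valid on that material, because the formula in Section 9.5.4 is for serum cystatin C. Retrieval and validation would be further costs, which the documents do not allow me to size.

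If neither is done, remove Week 96 eGFR-cystatin C from the two Synopsis entries (endpoints and safety analyses), Sections 11.1 and 11.6, and SAP 5.2.3.1: five text edits. As this would come after the Week 48 results, give the reason, namely that the sample was never scheduled. Reporting whatever values exist, with their number, would be transparent but would not estimate the endpoint for the arms.

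In either case, reconcile the general follow-up statement in Section 9.5.4 with the schedule.
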